8.2.3.2. Management of Immune-Mediated Adverse Events

Adverse events that meet the criteria for imAEs, as noted above in the Investigator's Brochure, should be reported as imAEs in the eCRF. If AEs corresponding to the common terms for imAEs are attributed as NOT related to cemiplimab by the investigator, additional information should be provided to substantiate an alternative attribution (eg, infectious diarrhea).

If not provided at the outset, this information may be requested by immediate edit checks or in subsequent queries. The sponsor may request additional information for any AE that is of a type known to be potentially immune-mediated (eg, rash, colitis, elevated transaminases, endocrine events), but is deemed not an imAE by the investigator.

Any grade 3 or greater imAE should be reported as an AESI (Section 10.2.3).

The following general principles apply to management of imAEs, unless otherwise specified in [Appendix 2](#):

Grade 1: Continue study treatment with close monitoring and provide symptomatic management

Grade 2: Consider withholding study treatment

Grade 3: Withhold study treatment

Grade 4: Discontinue study treatment

If cemiplimab is held for \leq grade 3 imAE, consider resuming when symptoms and/or laboratory values revert to baseline or \leq grade 1 after corticosteroid taper (typically, to ≤ 10 mg/day prednisone or equivalent).

Permanently discontinue study treatment for:

- Recurrent grade 3 imAEs
- Grade ≥ 3 or recurrent grade 2 Pneumonitis
- Grade ≥ 3 Hepatitis with AST/ALT $>5\times$ ULN or total bilirubin $>3\times$ ULN
- Grade ≥ 3 Nephritis with renal dysfunction
- Grade ≥ 3 Uveitis
- Grade ≥ 3 Neurologic toxicity
- Grade ≥ 3 Myocarditis or pericarditis
- Grade ≥ 3 Infusion related reaction
- Confirmed Stevens-Johnson syndrome (SJS), toxic epidermal necrolysis (TEN), or drug reaction with eosinophilia and systemic symptoms (DRESS)

- Grade ≥ 3 or recurrent grade 2 imAEs in patients previously treated with idelalisib
- Grade ≥ 3 infusion-related reaction
- Grade 2 or 3 imAEs persistent for ≥ 12 weeks after the last study treatment (excluding endocrinopathies)
- Requirement for ≥ 10 mg per day prednisone or equivalent lasting ≥ 12 weeks after the last study treatment

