Grade 1	• No change	• Monitor liver function tests (LFT) more frequently until resolution to baseline values	
Grade 2 with: Elevated ALT & AST >3 and \leq 5x ULN Or total bilirubin >1.5x and \leq 3x ULN	• Withhold study treatment until hepatitis improves and remains at grade 0 to 1 after corticosteroid taper to \leq 10 mg/day prednisone or equivalent or returns to baseline AST or ALT after completion of corticosteroid taper	
 Monitor LFT more frequently until resolution to baseline values Consider appropriate consultation with hepatologist and liver biopsy to establish etiology of hepatic injury, if necessary Consider inpatient monitoring for patients with ALT/AST >8x ULN and or elevated total bilirubin >3x ULN Treatment with systemic corticosteroids (1 to 2 mg/kg/day prednisone or equivalent) until resolution to \leq grade 1 and taper over at least 1 month If no improvement within 3 days after initiation of systemic steroids, consider additional immunosuppressive therapy ie, mycophenolate mofetil 0.5 to 1 g BID Several courses of steroid tapering may be necessary as symptoms may worsen when the steroid dose is decreased 	
 All attempts should be made to rule out other causes such as metastatic disease, progressive liver disease, viral hepatitis, alternative drug toxicity, infectious causes and/or myositis
Grade 3 or 4 with: Elevated ALT & AST >5x ULN or total bilirubin >3x ULN	• Permanently discontinue study treatment	• Same as above	

Recommended Adverse Events Management for Neurotoxicity

CTCAE v5.0 Grade	Study Treatment Management	Action & Supportive Care Guidelines	Diagnostic Considerations
Grade 1	• No change	
 • Closely monitor the patient • If worsening, treat as grade 2 or 3 to 4, as clinically appropriate 	
Grade 2	• Withhold study treatment until improves and remains at grade 0 to 1 after corticosteroid taper to ≤ 10 mg/day prednisone or equivalent	
 • Treat symptoms per local guidelines, eg 0.5 to 1 mg/kg/day methylprednisolone IV or oral (PO) equivalent • If worsening, treat as grades 3 to 4 • Consider neurology consult 	
 • If immune-mediated encephalitis is suspected, consider radiologic assessment and, if possible, cerebrospinal fluid (CSF) assessment for auto-immune antibodies

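### In the Appendix 2 Grade 2 hepatitis row, bilirubin alone can put a patient on hold, but the alternative release route is silent on bilirubin, so hold and release can both be met

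*Protocol*

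**What the plan says.** Appendix 2, hepatitis table, Grade 2 row, sets two alternative triggers. The first is "Grade 2 with: Elevated ALT & AST >3 and" up to 5x ULN. The second is "Or total bilirubin >1.5x and" up to 3x ULN, which needs no enzyme rise. The next row, permanent discontinuation, begins at "Elevated ALT & AST >5x ULN or total bilirubin >3x ULN".

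The Grade 2 hold can end in two ways. The first is "Withhold study treatment until hepatitis improves and remains at grade 0 to 1 after corticosteroid taper to" a prednisone equivalent of 10 mg/day or less. The second is "or returns to baseline AST or ALT after completion of corticosteroid taper".

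The action column of the same row reads "Treatment with systemic corticosteroids (1 to 2 mg/kg/day prednisone or equivalent) until resolution to" grade 1 or below, followed by a taper of at least a month. It also warns that symptoms can worsen as the dose comes down and that repeated tapers may be needed.

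Section 8.2.3.2 has a broader general rule, "consider resuming when symptoms and/or laboratory values revert to baseline" or to grade 1 or below, but it gives way to Appendix 2 where the appendix is specific. The general hold-and-resume paragraph opening Appendix 2 gives way to the event tables, and Section 8.2.4 gives way to whichever section is more detailed.

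**The concern.** A rule for restarting after a hold should deal with each finding that can start the hold. Here bilirubin is a sufficient trigger, yet one of the two release routes does not refer to it. The two clauses also combine the enzymes differently, so it is unclear whether one or both must recover.

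What is at stake is mainly patient safety. The protocol can tell a site both to withhold and that the condition for release is met, in a range that ends where permanent discontinuation begins. A secondary effect is that dose interruptions, exposure (SAP 5.6.2) and treatment-discontinuation summaries (SAP 5.4 and 5.8.1) could depend on which clause a site applies. Nothing here bears on the ORR analysis method.

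**Working it through.** The plan states no figure to reproduce. The check sets the clauses side by side and asks whether any patient state satisfies both.

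1. **Hold range (Grade 2 row).** ALT and AST >3x to ≤5x ULN, or total bilirubin >1.5x to ≤3x ULN.

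2. **Release by grade.** The row uses bilirubin to define grade 2, so a patient with bilirubin >1.5x ULN is not at grade 0 to 1. This route does not overlap with the hold range.

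3. **Release by enzymes.** It needs AST or ALT at baseline and a completed taper. Take ALT = AST = baseline and bilirubin = 2x ULN: the hold range is met through bilirubin, and so is the release clause. The overlap covers bilirubin >1.5x to ≤3x ULN, so its upper end is 3/1.5 = 2 times its lower end.

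4. **Enumeration.** Assume baseline AST = ALT = 1x ULN and a completed taper. Use ALT and AST values of 1, 2, 3, 3.5, 4 and 5, and bilirubin values of 1, 1.5, 1.6, 2, 2.5 and 3 (all x ULN), giving 6 × 6 × 6 = 216 states.
   - If the ampersand means both enzymes: 4 bilirubin values lie in the hold range (1.6, 2, 2.5, 3), and 6 + 6 − 1 = 11 enzyme pairs have at least one enzyme at baseline. Overlap = 4 × 11 = 44 states, all through bilirubin. The enzyme trigger adds none, because one enzyme at baseline defeats it.
   - If the ampersand means either enzyme: add 2 bilirubin values outside the hold range (1, 1.5) × 6 enzyme pairs (one enzyme at baseline, the other at 3.5, 4 or 5) = 12 states. Overlap = 44 + 12 = 56.
   - These counts show only that the overlap exists under both readings. They are not frequencies.

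5. **What the enzyme route adds.** Inclusion criterion 8e caps AST and ALT at 2.5x ULN, or 3x ULN with liver involvement. A return to baseline is therefore already below the enzyme hold range (>3x). Compared with release by grade, this route mainly adds cases where the other enzyme or bilirubin has not resolved. The same criterion admits bilirubin up to 3x ULN with liver involvement and makes an exception for documented Gilbert's syndrome, so bilirubin at entry can already lie in the hold range. The row does not say how a raised baseline bilirubin is to be handled.

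6. **Sequence within the row.** Steroids continue to grade 1 or below, then taper for at least a month. A patient managed this way starts the taper with bilirubin ≤1.5x ULN. Reaching the overlap then requires bilirubin to rise again during or after the taper, or a taper begun while bilirubin was unresolved. Release by grade requires the improvement to be maintained; release by enzymes does not.

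7. **Other rules.** Section 8.2.2.1 stops treatment permanently if a non-hematologic toxicity that led to a hold has not reached grade 1 or baseline within 12 weeks of the last infusion. Section 8.2.3.2 and the opening of Appendix 2 do so for grade 2 or 3 immune-mediated events persisting 12 weeks or more after the last treatment. A patient releasable through enzymes with bilirubin still at grade 2 may count as unresolved under all three.

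**The case against.** The strongest reply is that the row protects itself. The enzyme route opens only after a completed taper, and the taper starts only after resolution to grade 1 or below. A reader might infer that a bilirubin-triggered hold lapses as soon as the taper ends, with bilirubin never having improved; a patient managed according to the row would not get there. This stands and narrows the point. It does not close it, because the row itself expects worsening as steroids are reduced and the enzyme route has no bilirubin condition. The mention of repeated tapers points towards further treatment, but does not say the route is then unavailable.

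Second, returning to baseline presupposes having left it, so in a bilirubin-only case the enzyme route may be inapplicable and not automatically met. That is a fair reading, but it is not stated. A mixed case, where both rise and only the enzymes recover, still meets the clause.

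Third, a patient with bilirubin in the range is still in a row that says to withhold, and footnote 16 to the schedule of events allows chemistry to be drawn up to 72 hours before cemiplimab. Section 8.2.3.2 also preserves clinical judgment and lets investigators hold when hold criteria are not formally met. A reader might infer that the protocol compels a restart; it does not. Judgment does not, however, make the two clauses consistent across sites.

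Fourth, a reader might infer that release is possible with one enzyme still as high as 5x ULN while the enzyme trigger remains met. That holds only if the ampersand means either enzyme. If it means both, one enzyme at baseline takes the patient out of the enzyme trigger, although the other may still exceed 3x ULN.

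**Conclusion.** The inconsistency is real but limited. Total bilirubin alone can place a patient in the Grade 2 hold range, one of two release routes does not mention it, and the enzymes are combined differently in trigger and release. No general rule in Section 8.2.3.2, Section 8.2.4 or the Appendix 2 introduction supplies the missing condition, because each defers to the more specific table.

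The overlap spans bilirubin >1.5x to ≤3x ULN and exists under either reading of the ampersand. In practice it is confined mainly to patients whose bilirubin rises again during or after the taper, or does not resolve while an enzyme is at baseline. The documents give neither the incidence of Grade 2 hepatitis holds nor the share reaching this state. A count obtained by applying an assumed hold rate to 105 patients would describe all such holds, not the smaller group affected here. The number is likely small.

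The conclusion rests on reading the release routes as true alternatives, as written. It implies no view on which clinical rule is right. A wording correction is warranted because the rule governs restarting treatment next to a permanent-discontinuation boundary.

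**What to change.** At the next amendment, reconcile the trigger and release wording in the Grade 2 hepatitis row. State how bilirubin is treated in the alternative release route, whether one, all or only the triggering analytes must meet it, and whether the enzyme trigger means both enzymes or either. Align the result with the 12-week rules in Section 8.2.2.1, Section 8.2.3.2 and the opening of Appendix 2. The content of the rule is for the sponsor's medical team.

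In the same edit, check Section 9.2.3.6. It lets sites measure total or direct bilirubin according to local standard, although the hepatitis row is defined on total bilirubin.

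The text change is a sentence or so in the row plus matching phrases elsewhere. It may not be free of added testing: if total bilirubin is to be relied on, any site that reports only direct bilirubin would have to add it. No change to the sample size or the planned efficacy analyses is needed.

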APPENDIX 3. RESPONSE EVALUATION CRITERIA IN SOLID TUMORS: RECIST GUIDELINE (VERSION 1.1)

This appendix has been excerpted from the revised Response Evaluation Criteria in Solid Tumors (RECIST) guideline (version 1.1); ([Eisenhauer, 2009](#)). For full details pertaining to the RECIST 1.1 criteria, please refer to the publication.

1. Assessment of Tumor Burden Measurable Disease at Baseline

Overall tumor burden must be assessed at baseline and will be used as comparator for subsequent measurements. Tumor lesions will be characterized as measurable or non-measurable as follows:

Response and progression will be evaluated in this study using the international criteria proposed by the revised Response Evaluation Criteria in Solid Tumors (RECIST) guideline (version 1.1); ([Eisenhauer, 2009](#)). Changes in the largest diameter (unidimensional measurement) of the tumor lesions and the shortest diameter in the case of malignant lymph nodes are used in the RECIST criteria.

1.1. Measurable disease

- Tumor lesions must be accurately measured in at least one dimension (longest diameter in the plane of measurement is to be recorded) with a minimum size of
 - 10 mm by computed tomography (CT) or magnetic resonance imaging (MRI) scan (slice thickness recommended to be no greater than 5 mm)
 - 10 mm caliper measurement by clinical exam (lesions which cannot be accurately measured with calipers should be recorded as non-measurable)
- **Malignant lymph nodes:** To be considered pathologically enlarged and measurable, a lymph node must be ≥ 15 mm in short axis when assessed by CT or MRI scan (slice thickness recommended to be no greater than 5 mm). At baseline and in follow-up, only the short axis will be measured and followed.

1.2. Nonmeasurable Disease

All other lesions, including small lesions (longest diameter < 10 mm or pathological lymph nodes with ≥ 10 to < 15 mm short axis), are considered nonmeasurable disease. Bone lesions, leptomeningeal disease, ascites, pleural/pericardial effusions, lymphangitis cutis/pulmonitis, inflammatory breast disease, and abdominal masses (not followed by CT, MRI, or PET) are considered nonmeasurable.

1.2.1. Special Considerations

Bone lesions:

- Bone scan, PET scan or plain films are not considered adequate imaging techniques to measure bone lesions. However, these techniques can be used to confirm the presence or disappearance of bone lesions.
- Lytic bone lesions or mixed lytic-blastic lesions, with identifiable soft tissue components, that can be evaluated by cross sectional imaging techniques such as CT

or MRI can be considered measurable lesions if the soft tissue component meets the definition of measurability described above.

- Blastic bone lesions are non-measurable.

Cystic lesions:

Cystic lesions that meet the criteria for radiographically defined simple cysts should not be considered malignant lesions (neither measurable nor nonmeasurable) since they are, by definition, simple cysts. “Cystic lesions” thought to represent cystic metastases can be considered measurable lesions, if they meet the definition of measurability described above. However, if non-cystic lesions are present in the same patient, these are preferred for selection as target lesions.

Lesions with prior local treatment:

- Tumor lesions situated in a previously irradiated area, or in an area subjected to other locoregional therapy, are usually not considered measurable unless there has been demonstrated progression in the lesion.

1.3. Methods of Assessment

All measurements must be recorded in metric notation, using calipers if clinically assessed. All baseline evaluations should be performed as closely as possible to the beginning of treatment and never more than 4 weeks before the beginning of the treatment.

The same method of assessment and the same technique should be used to characterize each identified and reported lesion at baseline and during follow-up. Imaging-based evaluation is preferred to evaluation by clinical examination unless the lesion(s) being followed cannot be imaged but are assessable by clinical exam.

- **CT and MRI.** CT is the best currently available and reproducible method to measure lesions selected for tumor assessment. This guideline has defined measurability of lesions on CT scan based on the assumption that CT slice thickness is 5 mm or less. When CT scans have slice thickness greater than 5 mm, the minimum size for a measurable lesion should be twice the slice thickness. MRI is also acceptable for body scans except chest. MRI is preferred for brain scans.

1.4. Baseline Documentation of Target and Non-Target Lesions

Target lesions: When more than one measurable lesion is present at baseline all lesions up to a maximum of five lesions total (and a maximum of two lesions per organ) representative of all involved organs should be identified as target lesions and will be recorded and measured at baseline. Target lesions should be selected on the basis of their size (lesions with larger size are generally preferred), be representative of all involved organs, have better defined boundaries, and should lend themselves to reproducible repeated measurements.

Lymph nodes merit special mention since they are normal anatomical structures which may be visible by imaging even if not involved by tumor. Pathological nodes which are defined as measurable and may be identified as target lesions must meet the criterion of a short axis of ≥ 15 mm by CT or MRI scan. Only the short axis of these nodes will contribute to the baseline sum. All other pathological nodes (those with short axis ≥ 10 mm but < 15 mm) should be

considered non-target lesions. Nodes that have a short axis <10 mm are considered non-pathological and should not be recorded or followed.

A sum of the diameters (longest for non-nodal lesions, short axis for nodal lesions) for all target lesions will be calculated and reported as the baseline sum diameters. The baseline sum of diameters will be used as reference to further characterize any objective tumor regression in the measurable dimension of the disease.

Non-target lesions: All other lesions (or sites of disease) including pathological lymph nodes should be identified as non-target lesions and should also be recorded at baseline. Measurements of these lesions are not required, but the presence, absence, or, in rare cases, unequivocal progression of each should be noted throughout follow-up. In addition, it is possible to record multiple non-target lesions involving the same organ as a single item on the case record form (e.g., ‘multiple enlarged pelvic lymph nodes’ or ‘multiple liver metastases’).

1.5. Response Criteria

This section provides the definitions of the criteria used to determine objective tumor response for target and non-target lesions.

1.5.1. Evaluation of Target Lesions

- **Complete Response (CR):** Disappearance of all target lesions. Any pathological lymph nodes (whether target or non-target) must have reduction in short axis to <10 mm (<1 cm).
- **Partial Response (PR):** At least a 30% decrease in the sum of the diameters of target lesions, taking as reference the baseline sum diameters.
- **Progressive Disease (PD):** At least a 20% increase in the sum of the diameters of target lesions, taking as reference the smallest sum on study (this includes the baseline sum if that is the smallest on study). In addition to the relative increase of 20%, the sum must also demonstrate an absolute increase of at least 5 mm (0.5 cm). (**Note:** the appearance of one or more new lesions is also considered progression).
- **Stable Disease:** Neither sufficient shrinkage to qualify for PR nor sufficient increase to qualify for progressive disease, taking as reference the smallest sum diameters while on study.

Special notes on the assessment of target lesions:

- Lymph nodes: Lymph nodes identified as target lesions should always have the actual short axis measurement recorded and should be measured in the same anatomical plane as the baseline examination, even if the nodes regress to below 10 mm on study. This means that when lymph nodes are included as target lesions, the ‘sum’ of lesions may not be zero even if complete response criteria are met, since a normal lymph node is defined as having a short axis of <10 mm.
- Target lesions that become ‘too small to measure’: All lesions (nodal and non-nodal) recorded at baseline should have their actual measurements recorded at each subsequent evaluation, even when very small (eg, 2 mm). If the radiologist is able to provide an actual measure, that should be recorded, even if it is below 5 mm. However,

when such a lesion becomes difficult to assign an exact measure to then: (i) if it is the opinion of the radiologist that the lesion has likely disappeared, the measurement should be recorded as 0 mm. (ii) if the lesion is believed to be present and is faintly seen but too small to measure, a default value of 5 mm should be assigned (note: in case of a lymph node believed to be present and faintly seen but too small to measure, a default value of 5 mm should be assigned in this circumstance as well). This default value is derived from the 5 mm CT slice thickness (but should not be changed with varying CT slice thickness).

- Lesions that split or coalesce on treatment: When non-nodal lesions ‘fragment’, the longest diameters of the fragmented portions should be added together to calculate the target lesion sum. Similarly, as lesions coalesce, a plane between them may be maintained that would aid in obtaining maximal diameter measurements of each individual lesion. If the lesions have coalesced such that they are no longer separable, the vector of the longest diameter in this instance should be the maximal longest diameter for the ‘coalesced lesion’.

1.5.2. Evaluation of Non-Target Lesions

While some non-target lesions may actually be measurable, they need not be measured and instead should be assessed only qualitatively at the time points specified in the protocol.

- **Complete Response:** Disappearance of all nontarget lesions and normalization of tumor marker level. All lymph nodes must be nonpathological in size (<10 mm short axis).
- **Non-CR/Non-PD:** Persistence of one or more nontarget lesion(s) and/or maintenance of tumor marker level above the normal limits.
- **Progressive Disease:** Appearance of one or more new lesions and/or unequivocal progression of existing nontarget lesions. Unequivocal progression should not normally trump target lesion status. It must be representative of overall disease status change, not a single lesion increase.

Although a clear progression of “nontarget” lesions only is exceptional, the opinion of the treating physician should prevail in such circumstances, and the progression status should be confirmed at a later time by the review panel (or investigator).

